See Disclosures and Management of Personal Interests in Human Research
<http://www.yale.edu/hrpp/policies/index.html#COI>

Yes No

Do you or does anyone on the research team who is determined by you to be responsible for the design, conduct or reporting of this research have any patent (sole right to make, use or sell an invention) or copyright (exclusive rights to an original work) interests related to this research protocol?

Yes No

If yes to either question above, list names of the investigator or responsible person:

The Yale University Principal Investigator, all Yale University co-investigators, and all Yale University individuals who are responsible for the design, conduct or reporting of research must have a current financial disclosure form on file with the University's Conflict of Interest Office. Yale New Haven Hospital personnel who are listed as co-investigators on a protocol with a Yale University Principal Investigator must also have a current financial disclosure form on file with the University's Conflict of Interest Office. If this has not been done, the individual(s) should follow this link to the COI Office Website to complete the form: <http://www.yale.edu/coi/>

NOTE: The requirement for maintaining a current disclosure form on file with the University's Conflict of Interest Office extends primarily to Yale University and Yale-New Haven Hospital personnel. **Whether or not they are required to maintain a disclosure form with the University's Conflict of Interest Office, all investigators and individuals deemed otherwise responsible by the PI who are listed on the protocol are required to disclose to the PI any interests that are specific to this protocol.**

SECTION II: GENERAL INFORMATION

1. Performing Organizations: Identify the hospital, in-patient or outpatient facility, school or other agency that will serve as the location of the research. Choose all that apply:

a. Internal Location[s] of the Study:

- | | |
|--------------------------------------------------------------------------|------------------------------------------------------------------|
|  Magnetic Resonance Research Center
(MR-TAC) |  Yale University PET Center |
|  Yale Cancer Center/Clinical Trials Office (CTO) |  YCCI/Church Street Research Unit (CSRU) |
|  Yale Cancer Center/Smilow |  YCCI/Hospital Research Unit (HRU) |
| |  YCCI/Keck Laboratories |

- Yale-New Haven Hospital
 Cancer Data Repository/Tumor Registry
 Specify Other Yale Location:

Yale-New Haven Hospital—Saint Raphael Campus

b. External Location[s]:

- | | |
|------------------------------------------------------------------------------|----------------------------------------------------------------|
|  APT Foundation, Inc. |  Haskins Laboratories |
|  Connecticut Mental Health Center |  John B. Pierce Laboratory, Inc. |
|  Clinical Neuroscience Research Unit (CNRU) |  Veterans Affairs Hospital, West Haven |
|  Other Locations, Specify:
(Specify location(s)): |  International Research Site |

c. Additional Required Documents (check all that apply):

- | | |
|---------------------------------------------------------------------------------------------------------------------------------------------------------------------------------------------------------------------------------------|----------------|
|  *YCCI-Scientific and Safety Committee (YCCI-SSC) | X N/A |
|  *Pediatric Protocol Review Committee (PPRC) | Approval Date: |
|  *YCC Protocol Review Committee (YRC-PRC) | Approval Date: |
|  *Dept. of Veterans Affairs, West Haven VA HSS | Approval Date: |
|  *Radioactive Drug Research Committee (RDRC) | Approval Date: |
|  YNHH-Radiation Safety Committee (YNHH-RSC) | Approval Date: |
|  Yale University RSC (YU-RSC) | Approval Date: |
|  Magnetic Resonance Research Center PRC (MRRC-PRC) | Approval Date: |
|  *Nursing Research Committee | Approval Date: |
|  YSM/YNHH Cancer Data Repository (CaDR) | Approval Date: |
|  Dept. of Lab Medicine request for services or specimens form | |
|  Imaging on YNHH Diagnostic Radiology equipment request form (YDRCTO request) found at
http://radiology.yale.edu/research/ClinTrials.aspx | |

**Approval from these committees is required before final HIC approval is granted. See instructions for documents required for initial submission and approval of the protocol. Allow sufficient time for these requests. Check with the oversight body for their time requirements.*

2. **Probable Duration of Project:** State the expected duration of the project, including all follow-up and data analysis activities.

-1 year

3. **Research Type/Phase: (Check all that apply)**

a. **Study Type**

- Single Center Study
 Multi-Center Study

Does the Yale PI serve as the PI of the multi-site study? Yes No

- Coordinating Center/Data Management
 Other:

b. **Study Phase** X N/A

Pilot Phase I Phase II Phase III Phase IV
 Other (Specify)

4. **Area of Research: (Check all that apply)** Note that these are overlapping definitions and more than one category may apply to your research protocol. Definitions for the following can be found in the instructions section 4c:

X Clinical Research: Patient-Oriented Clinical Research: Outcomes and Health Services
 Clinical Research: Epidemiologic and Behavioral Interdisciplinary Research
 Translational Research #1 ("Bench-to-Bedside") Community-Based Research
 Translational Research #2 ("Bedside-to-Community")

5. Is this study a clinical trial? Yes X No

NOTE the current ICMJE (International Committee of Medical Journal Editors) definition of a clinical trial: "any research study that prospectively assigns human participants or groups of humans to one or more health-related interventions to evaluate the effects on health outcomes." Health-related interventions include any intervention used to modify a biomedical or health-related outcome (for example, drugs, surgical procedures, devices, behavioral treatments, dietary interventions, and process-of-care changes). Health outcomes include any biomedical or health-related measures obtained in patients or participants, including pharmacokinetic measures and adverse events"

If yes, where is it registered?

Clinical Trials.gov X
 Other (Specify)

Registration of clinical trials at their initiation is required by the FDA, NIH and by the ICMJE.

If this study is registered on clinicaltrials.gov, there is new language in the consent form and compound authorization that should be used.

For more information on registering clinical trials, including whether your trial must be registered, see the YCCI webpage, <http://ycci.yale.edu/researchers/ors/registerstudy.aspx> or contact YCCI at [contact])

6. Does the Clinical Trials Agreement (CTA) require compliance with ICH GCP (E6)?
 Yes X No

7. Will this study have a billable service? *A billable service is defined as any service rendered to a study subject that, if he/she was not on a study, would normally generate a bill from either Yale-New Haven Hospital or Yale Medical Group to the patient or the patient's insurer. The service may or may not be performed by the research staff on your study, but may be provided by professionals within either Yale-New Haven Hospital or Yale Medical Group (examples include x-rays, MRIs, CT scans, specimens sent to central labs, or specimens sent to pathology). Notes: 1. There is no distinction made whether the service is paid for by the subject or their insurance*

(Standard of Care) or by the study's funding mechanism (Research Sponsored). 2. This generally includes new services or orders placed in EPIC for research subjects.

Yes No

If answered, "yes", this study will need to be set up in OnCore, Yale's clinical research management system, for Epic to appropriately route research related charges. Please contact [contact]

8.. Are there any procedures involved in this protocol that will be performed at YNHH or one of its affiliated entities? Yes No *If Yes, please answer questions a through c and note instructions below. If No, proceed to Section III.*

a. Does your YNHH privilege delineation currently include the **specific procedure** that you will perform? **Yes**

b. Will you be using any new equipment or equipment that you have not used in the past for this procedure? **NO**

c. Will a novel approach using existing equipment be applied? **NO**

If you answered "no" to question 8a, or "yes" to question 8b or c, please contact the YNHH Department of Physician Services ([name]) for prior approval before commencing with your research protocol.

Please note that if this protocol includes Yale-New Haven Hospital patients, including patients at the HRU, the Principal Investigator and any co-investigators who are physicians or mid-level practitioners (includes PAs, APRNs, psychologists and speech pathologists) who may have direct patient contact with patients on YNHH premises must have medical staff appointment and appropriate clinical privileges at YNHH. If you are uncertain whether the study personnel meet the criteria, please telephone the Physician Services Department at [contact]. By signing this protocol as a PI, you attest that you and any co-investigator who may have patient contact has a medical staff appointment and appropriate clinical privileges at YNHH.

SECTION III: FUNDING, RESEARCH TEAM AND TRAINING

1. **Funding Source:** Indicate all of the funding source(s) for this study. Check all boxes that apply.

Provide information regarding the external funding source. This information should include identification of the agency/sponsor, the funding mechanism (grant or contract), and whether the award is pending or has been awarded. Provide the M/C# and Agency name (if grant-funded). If the funding source associated with a protocol is "pending" at the time of the protocol submission to the HIC (as is the case for most NIH submissions), the PI should note "Pending" in the appropriate section of the protocol application, provide the M/C# and Agency name (if grant-funded) and further note that University (departmental) funds support the research (until such time that an award is made).

PI	Title of Grant	Name of Funding Source	Funding	Funding Mechanism
[name]			 Federal  State  Non Profit  Industry  Other For Profit  Other	 Grant-M#  Contract#  Contract Pending  Investigator/Department Initiated  Sponsor Initiated  Other, Specify: Dept of Orthopedic Surgery

As Chair, do you have any real or apparent protocol-specific conflict of interest between yourself and the sponsor of the research project, or its competitor or any interest in any intervention and/or method tested in the project that might compromise this research project?

Yes (provide a description of that interest in a separate letter addressed to the HIC)

No

I assure the HIC that the principal investigator and all members of the research team are qualified by education, training, licensure and/or experience to assume participation in the conduct of this research trial. I also assure that the principal investigator has departmental support and sufficient resources to conduct this trial appropriately.

Chair Name (PRINT) and Signature

Date

Department

YNHH Human Subjects Protection Administrator Assurance Statement

Required when the study is conducted solely at YNHH by YNHH health care providers.

As Human Subject Protection Administrator (HSPA) for YNHH, I certify that:

- I have read a copy of the protocol and approve it being conducted at YNHH.
- I agree to notify the IRB if I am aware of any real or apparent institutional conflict of interest.
- The principal investigator of this study is qualified to serve as P.I. and has the support of the hospital for this research project.

YNHH HSPA Name (PRINT) and Signature

Date

SECTION V: RESEARCH PLAN**1. Statement of Purpose:** State the scientific aim(s) of the study, or the hypotheses to be tested.

The primary objective of this study is to assess the safety and efficacy of Tranexamic acid (TXA) in reducing blood loss and transfusion requirements for patients with osteoporotic hip fractures. In addition to assessing blood loss in these patients, complications associated with TXA use would be characterized including systemic (pulmonary embolism, deep venous thrombosis, myocardial infarction, stroke) and surgical site (hematoma, infection) events, need for re-hospitalization or re-operation and 30 day mortality.

2. Background: Describe the background information that led to the plan for this project.

Provide references to support the expectation of obtaining useful scientific data.

Hip fractures are associated with significant blood loss and a subsequent need for blood transfusion. The causes of bleeding are multifactorial, increased fibrinolytic activity being one of them.^{1, 2} The use of allogenic blood products is expensive and is associated with increased risk of hemolytic and anaphylactic reactions, post-operative infections¹ and lengthened hospital stay. Tranexamic acid (TXA) is a simple and inexpensive pharmacologic agent that inhibits fibrinolysis and reduced bleeding.^{1, 2} It has a 44 year history of clinical use beginning with patients with symptomatic menorrhagia as well as bleeding prophylaxis in hemophiliac patients undergoing tooth extraction

TXA is an antifibrinolytic medication (reduces the destruction of blood clots, thus promoting the ability to stop bleeding) that is frequently used to reduce perioperative blood loss, blood transfusions and associated costs in major cardiac, vascular, obstetric, and orthopedic procedures. It has been used successfully in orthopedics to reduce perioperative blood loss, particularly in spine surgery^{5, 6, 7} total knee and total hip arthroplasty (THA)^{9,10}. Multiple recent meta-analyses have found that use of TXA in the setting of total knee arthroplasty (TKA) and THA leads to significantly less overall blood loss and lower rates of blood transfusion without increasing rates of venous thromboembolism (VTE) or other complications^{11,12}.

Osteoporotic hip fractures are at an increased risk for acute blood loss than elective orthopaedic surgery patients because they are exposed to a double bleeding insult. Fractures bleed and many of these patients sustain their first hit when hematoma forms in their soft

tissues leading to symptomatic anemia. Subsequently these patients sustain additional blood loss when they undergo surgery for definitive treatment of their injuries.

Trauma surgeons understand the risk of hemorrhage associated with trauma and routinely give TXA to patients who present with high energy injuries. The CRASH-2 trial was an international study which randomized 20,000 bleeding trauma patients to get IV TXA or matching placebo upon presentation. With 99.5% follow up, the authors noted a decreased risk of bleeding and death without ill effect.¹³

Although several previous studies have used IV TXA to reduce blood loss, TXA has proved to be an effective antifibrinolytic agent in IV, topical and oral formulations. Oral preparations of the drug may be preferred due to their equivalent efficacy and lower cost.¹⁴

There are limited data the use of TXA in patients with hip fractures. We propose a double-blinded, randomized, controlled trial comparing perioperative administration of TXA to placebo in the setting of hip fractures. Thus our goal is to examine the safety and efficacy of TXA in reducing blood loss and red blood cell requirement for patients with hip fractures at the time of hospital admission.

Informed consent will be obtained from the patient or health care proxy upon diagnosis of hip fracture by the orthopedic consult resident or research coordinator. At that time, study subjects will be randomized to two groups. The two patient groups will include:

1. 1.95g of oral tranexamic acid upon presentation to the emergency department and again 2 hours prior to surgery.
2. Placebo tablets in the emergency department and again 2 hours prior to surgery.

Pharmacy will keep the surgeon blinded to the treatment group that the patient is randomized into. Blood loss following surgery will be evaluated during the entire in-patient stay of the study subjects. Patients will also be surveyed about related complications and/or re-hospitalizations at their first postoperative office visit (2-3 weeks post-operative).

2. Sculco TP. Global blood management in orthopaedic surgery. *Clin Orthop Relat Res* 1998;357:43-9
5. Cherian T, Maier S P II, Bianco K, et al. Efficacy of tranexamic acid on surgical bleeding in spine surgery: a meta-analysis. *Spine J.* 2015;15(4):752–761.

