Additional data being collected include hospital length of stay, patient demographics including ASA class. Complications will be recorded as they occur or at 2 and 6 week follow up. Both of these visits will be in-person at their scheduled follow up clinic appointments.

Genetic Testing N/A X

A. Describe

- the types of future research to be conducted using the materials, specifying if immortalization of cell lines, whole exome or genome sequencing, genome wide association studies, or animal studies are planned
 - the plan for the collection of material or the conditions under which material will be received
 - the types of information about the donor/individual contributors that will be entered into a database
 - the methods to uphold confidentiality
- B. What are the conditions or procedures for sharing of materials and/or distributing for future research projects?
- C. Is widespread sharing of materials planned?
- D. When and under what conditions will materials be stripped of all identifiers?
- E. Can donor-subjects withdraw their materials at any time, and/or withdraw the identifiers that connect them to their materials?
- How will requests to withdraw materials are handled (e.g., material no longer identified: that is, anonymized) or material destroyed?
- F. Describe the provisions for protection of participant privacy
- G. Describe the methods for the security of storage and sharing of materials

4. **Subject Population:** Provide a detailed description of the types of human subjects who will be recruited into this study.

- Adults 18 years and older. There is no upper age limit.
- Femoral neck and intertrochanteric femur fractures who present to the emergency department after a low energy mechanism. Low energy injuries result in fractures in patients whose bone integrity is compromised after a mechanism which would not have otherwise fractured healthy bone. An example is a fall from standing in a patient with osteoporotic bone.
- Osteoporotic hip fractures

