- increased risk of seizures and with renal complications following their use in cardiac surgery.
- may increase risk of disseminated intravascular coagulation (DIC).
- need for caution in the use of these agents in patients with hematological malignancies as they are at increased risk of DIC
-

Adverse Events

An adverse event (AE) is any noxious, unintended, or untoward medical occurrence occurring at any dose that may appear or worsen in a subject during the course of a study. It may be a new intercurrent illness, a worsening concomitant illness, an injury, or any concomitant impairment of the subject's health, including laboratory test values (as specified by the criteria below), regardless of etiology. Any medical condition that was present, prior to study treatment and that remains unchanged or improved should not be recorded as an AE. If there is a worsening of that medical condition, this should be considered an AE. A diagnosis or syndrome should be recorded as an AE rather than the individual signs or symptoms of the diagnosis or syndrome.

All AEs will be recorded by the Investigator(s) from signature of the informed consent form through 6 week post-operative period. AEs will be recorded on the data collection form. All AEs will be followed until resolved. Any AEs uncovered during routine postoperative care visits or review of the EMR will also be reported for study purposes.

Project specific AEs Exempt From Reporting

Certain adverse events would be expected to occur in hip fracture patients regardless of the use of the investigational product TXA. Therefore, within the post-surgical period, the following adverse events will be excluded from collection unless they are of a severity or frequency greater than would be expected for this post-surgical patient population.

- Intraoperative fracture
 - Uncommon
 - Higher risk in revision setting
- Hematoma
 - Low risk with postoperative drains
- Infection
 - Reported risk 1-10%
 - May be higher in rheumatoid
 - Higher in revision setting
- Implant Failure
 - Uncommon
- Medical risks
 - Blood transfusion reaction

- Pneumonia

However, the PI will report the following adverse events that can occur during the post-op period:

- Myocardial infarction
- Stroke
- Deep venous thrombosis
- Pulmonary embolus
- Death

Abnormal laboratory values defined as adverse events

An abnormal laboratory value is considered to be an AE if the laboratory abnormality is characterized by any of the following:

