If a specific event is not included in the NCI CTCAE toxicity scale, the following scale will be used to grade the event:

Grade	Definition
1	Mild Awareness of sign, symptom, or event, usually transient, requiring no special treatment and generally not interfering with usual daily activities
2	Moderate Discomfort that causes interference with usual activities; usually ameliorated by basic therapeutic maneuvers
3	Severe Incapacitating with inability to do usual activities or significantly affects clinical status and warrants intervention. Hospitalization may or may not be required
4	Life-threatening Immediate risk of death; requires hospitalization and clinical intervention.
5	Death

Classification of Relationship/Causality of adverse events (AE/SAE) to study drug

The investigator will determine the relationship between the administration of study drug and the occurrence of an AE/SAE as not suspected or suspected as defined below:

Not suspected: The temporal relationship of the adverse event to study drug administration makes a **causal relationship unlikely or remote**, or other medications, therapeutic interventions, or underlying conditions provide a sufficient explanation for the observed event

Suspected: The temporal relationship of the adverse event to study drug administration makes a **causal relationship possible**, and other medications, therapeutic interventions, or underlying conditions do not provide a sufficient explanation for the observed event.

Unknown The temporal relationship of the adverse event to study drug administration makes a causal relationship unable to determine or unknown

Monitoring and reporting of adverse events

All subjects will be monitored for AEs between the signing of the informed consent and 6 weeks postop. Assessments may include monitoring of any or all of the following parameters: the subject's clinical symptoms; laboratory, pathological, radiological, or surgical findings; physical

examination findings; or other appropriate tests and procedures. Any AEs uncovered during routine postoperative care visits will be reported for study purposes.

9. Minimizing Risks: Describe the manner in which the above-mentioned risks will be minimized.

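### Follow-up for re-hospitalisation and re-operation is described inconsistently, and no step finds deaths or outside readmissions in patients who miss the clinic visits

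*Combined protocol and SAP*

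**What the plan says.** Section V.1 (Statement of Purpose) makes safety part of the primary objective. Besides thromboembolic, cardiac and surgical-site events, it names "need for re-hospitalization or re-operation and 30 day mortality" among the outcomes to be characterised.

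Three places then describe how events after discharge are found.

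- Section V.2 (Background): patients will be "surveyed about related complications and/or re-hospitalizations at their first postoperative office visit", which it places two to three weeks after surgery.
- Section V.3 (Research Plan): "Complications will be recorded as they occur or at 2 and 6 week follow up". It adds: "Both of these visits will be in-person at their scheduled follow up clinic appointments". Re-hospitalisation and re-operation are not mentioned here.
- Section V.8 (Risks, under Adverse Events): "All AEs will be recorded by the Investigator(s) from signature of the informed consent form through 6 week post-operative period", with a further source: "Any AEs uncovered during routine postoperative care visits or review of the EMR will also be reported for study purposes". The monitoring paragraph later in that section repeats the window: "All subjects will be monitored for AEs between the signing of the informed consent and 6 weeks postop". Inpatient hospitalisation is one of the criteria for a serious adverse event.

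Section V.8 also lists events exempt from collection unless they are more severe or more frequent than expected in this population. The list includes haematoma, infection, implant failure and pneumonia. Myocardial infarction, stroke, deep venous thrombosis, pulmonary embolus and death are to be reported.

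**The concern.** Re-hospitalisation, re-operation and death within 30 days are stated outcomes of a trial rated above minimal risk, so each needs a defined way of being found in every randomised patient. The Background and the Research Plan give different contact points, and only the Background ties a contact to re-hospitalisation. Staff who follow one section would ask different questions at different times from staff who follow the other.

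The second worry is who gets seen. Both visits are in person. A patient who has died cannot attend, and one who has been readmitted elsewhere or moved to a nursing facility may not. If events in such patients go uncounted, the reported safety rates are too low. In a trial of 50, a single event is visible in the rates.

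**Working it through.** The plan states no figure on this point, so there is none to reproduce. The check sets the sections side by side and converts the visit times to days after surgery: 2 × 7 = 14, 3 × 7 = 21 and 6 × 7 = 42.

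| Place | Complications | Re-hospitalisation | Re-operation | Last time point |
|---|---|---|---|---|
| Section V.2 | asked at first visit | asked at first visit | not mentioned | day 14 to 21 |
| Section V.3 | as they occur, or at 2 and 6 weeks | not mentioned | not mentioned | day 42 |
| Section V.8 | recorded, apart from the exempt list | only as a criterion for seriousness | not named; some would count as important medical events | day 42 |

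**Step 1, attenders and day 30.** The Research Plan visit and the adverse event window end at day 42, and 42 − 30 = 12. A patient seen at six weeks is therefore known to have survived past day 30. The plan does not say from which day the 30 days count. Randomisation precedes surgery, so six weeks after surgery is beyond day 30 from either start.

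**Step 2, the scheduled questions.** The only stated question about re-hospitalisation falls at day 14 to 21. The adverse event window continues for another 42 − 21 = 21 to 42 − 14 = 28 days. In that stretch a readmission must be volunteered, noticed in the record, or captured as a serious adverse event. Re-operation has no scheduled question at any time.

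**Step 3, the adverse event route.** A serious adverse event is first an adverse event. The plan does not say whether a readmission or re-operation is recorded when its cause is on the exempt list. Haematoma and infection are on that list, yet Section V.1 names both as outcomes. Implant failure is also there and is an obvious reason to re-operate. A readmission might be judged more severe than expected and so be collected, but that is left to case-by-case judgement.

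**Step 4, non-attenders.** No section describes a telephone call after a missed visit, a check of vital status, or a search of outside hospital records. Review of the electronic record is mentioned without timing, and it shows only what has been entered there.

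**Step 5, what a missed event does.** Section VII.1 gives a target of 50. Equal allocation is an assumption, since no ratio is stated. With 50 / 2 = 25 per arm, one missed event moves that arm's rate by 1/25 = 4 percentage points, and the trial-wide rate by 1/50 = 2 points. If both arms detect events with the same probability s, true risks p1 and p0 appear as s·p1 and s·p0. The ratio is unchanged, but the difference shrinks to s(p1 − p0) and both absolute rates are too low.

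**The case against.** A reader might infer that follow-up ends at the first office visit, leaving 30 − 21 = 9 to 30 − 14 = 16 of the 30 days unobserved. The documents do not support that. The Background sentence does not say that the survey happens only once, and calling the visit the first implies others. The Research Plan adds recording as events occur and a six-week visit, and Section V.8 adds a six-week window and record review. The 9 to 16 days appear only if the Background is read alone.

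A reader might also apply a 30-day limit to readmission. Section V.1 attaches 30 days to mortality only, and readmission and re-operation have no stated window.

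Nor do the documents say that events are recorded solely at in-person visits, or that the arms can be compared only among attenders. Patients and surgeons are blinded, and recording as events occur does not formally depend on attendance. That makes a lower rate in both arms more likely than a bias towards one arm. The documents give no figure for non-attendance, discharge to nursing facilities or readmission elsewhere, so selective loss of sicker patients is a reasonable assumption and not a demonstrated fact.

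All of this stands, and it narrows the point. It does not supply a question about re-hospitalisation or re-operation after the first visit, settle how the exempt list treats a readmission, or provide a way to learn the status of someone who does not come back.

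**Conclusion.** The point holds in a limited form. For patients who attend, the six-week visit and adverse event window cover day 30 with 12 days to spare. Two gaps remain. Re-hospitalisation and re-operation after the first visit have no dependable capture route, especially when the cause is on the exempt list. For patients who miss the visits, death by day 30 and readmission elsewhere are found only if they reach the electronic record.

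How many events would be lost cannot be worked out from the documents. The 4 percentage points per missed event rests on equal allocation of the 50 and says nothing about how likely a miss is. This is a data-collection weakness in a stated safety objective, and it is worth correcting because the correction is cheap. It does not bear on the blood-loss or in-hospital transfusion results.

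**What to change.** 1. Align Section V.2 with Section V.3, so that complications, re-hospitalisation and re-operation are each asked about at both the two-week and six-week visits.
2. Count these outcomes over the existing six-week window for every randomised patient. State that a readmission or re-operation is recorded whether or not its cause is on the exempt list in Section V.8.
3. Establish vital status at day 30 for every randomised patient, and state the day from which the 30 days count. Attendance at six weeks settles survival; otherwise use the contact in item 4 and record the date of any death.
4. If a visit is missed, telephone the patient or proxy and check the record. Section VIII already lists telephone numbers among the data collected, and Section V.7 already allows surrogate consent by telephone.

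The cost is protocol wording, a few fields on the data collection form and a few telephone calls by existing staff. Treatment and sample size are unaffected.
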